The theoretical adverse effects from tenapanor treatment in ESRD patients would be due to exaggerated pharmacological effects and may include electrolyte disturbances, metabolic acidosis, soft stools/diarrhea and reduced blood pressure. While a softening/loosening of the stool with an increased fluid loss via the intestine is an intended and desired effect of tenapanor in some patients, sensitive patients should be monitored for signs of dehydration in case of prolonged severe diarrhea. This study protocol includes clinical laboratory tests (including bicarbonate and electrolytes) and vital signs as well as specific discontinuation criteria related to phosphate control to mitigate risks to study participants as well as to reduce the risk for severe hyper- or hypophosphatemia during the study and limit the period with risk for suboptimal phosphate control. All patients will re-start their pre-study treatment with phosphate binders when their participation in the study ends. ESRD-HD patients are dialyzed three times per week

and their health status is checked at each visit as part of standard of care. See the Investigators Brochure for details on non-clinical and clinical results with tenapanor.

Patients will be informed both verbally and in writing about these aspects before taking part in any study-specific examination and the study will be conducted under conditions that ensure a high probability for the early detection of untoward events and for appropriate intervention.

In summary, the risks to the participants in this up to one year study are considered acceptable and the study results will be important for the development of a potential new drug, which could improve the treatment of hyperphosphatemia in this patient group.

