### 7.3.5 Analysis of Clinical Laboratory Tests

A certified laboratory will be used to process and provide results for the clinical laboratory tests. The baseline laboratory test results for clinical assessment for a particular test will be defined as the last measurement prior to the initial dose of study drug or active control.

For any laboratory test value outside the reference range that the Investigator considers clinically significant, the Investigator will:

- Repeat the test to verify the out-of-range value.
- Follow the out-of-range value to a satisfactory clinical resolution.
- Record as an AE any laboratory test value that (1) is confirmed and the Investigator considers clinically significant, or (2) that requires a patient to be discontinued from the study, or (3) that requires a patient to receive treatment, or (4) fulfills one or more SAE criteria.

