**8.13 Unscheduled visits**

Unscheduled visits, for missed scheduled visits or safety or tolerability related reasons are allowed. Procedures performed are at the discretion of the Investigator.

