**9.4 Statistical Methods**

**9.4.1 General Approach**

Descriptive statistics including the number of observations, mean, standard deviation, median, minimum, and maximum will be presented for continuous variables. Frequency and percentage of patients will be presented for categorical variables. Continuous variables will be analyzed using analysis of variance (ANOVA) or analysis of covariance (ANCOVA). Categorical variables will be analyzed using a Cochran-Mantel-Haenszel (CMH) test or a Pearson's Chi-square test.

Safety analyses will be performed on all patients enrolled in this study, while efficacy analyses will be performed only on those patients who are randomized to receive tenapanor

in the 26-week treatment period (i.e., patients treated with active control will not be included in any efficacy analyses).

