#### 9.4.7 Visit Windows

No analysis visit windows will be formally defined. The schedule of events in [Section 1.3](#) details the intended collection of study variables at specified visits. Should additional data be collected between scheduled visits, these data will be included in the patient data listings but ignored for analyses purposes, unless the additional data is the last data collected during each study period.

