#### 9.4.8 Safety Analyses

Safety analyses include summaries for adverse events, safety laboratory tests, vital signs, body weights, 12-lead ECGs, and physical examinations. These summaries will be provided for each study period separately.

Adverse events will be coded using the Medical Dictionary for Regulatory Activities (MedDRA). Summary tables and listings will be provided by system organ class and preferred term for each treatment (including dose, if applicable) group for treatment-emergent adverse events (TEAEs). Actual values and change from baseline values for clinical laboratory tests, vital signs, body weights, and ECGs will be summarized by treatment (including dose, if applicable) group for each visit. The number and percentage of patients in each physical examination category will be presented by treatment (including dose, if applicable) group for each visit.

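### No table counts patients with abnormal bicarbonate, electrolytes or blood pressure, and unscheduled values stay out of the summaries unless they are the last in the period

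*Combined protocol and SAP*

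**What the plan says.** Section 2.5 (Risk-Benefit Assessment) lists the theoretical harms, which "may include electrolyte disturbances, metabolic acidosis, soft stools/diarrhea and reduced blood pressure". It cites laboratory tests, including bicarbonate and electrolytes, and vital signs as part of the mitigation. Safety and tolerability is the first primary objective (3.1), a long-term safety comparison with sevelamer is a secondary objective (3.2), and the sevelamer arm is there for safety analysis (4.1).

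The planned output for these measures is in 9.4.8: "Actual values and change from baseline values for clinical laboratory tests, vital signs, body weights, and ECGs will be summarized by treatment" group and visit, separately for each study period. Section 9.4.1 fixes the content: "Descriptive statistics including the number of observations, mean, standard deviation, median, minimum, and maximum will be presented for continuous variables". Section 9.4.8 gives patient numbers and percentages for physical examination categories, but not for laboratory values or blood pressure.

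On data taken between scheduled visits, 9.4.7 says "these data will be included in the patient data listings but ignored for analyses purposes, unless the additional data is the last data collected" in a study period. The protocol expects such data. Section 8.13 states: "Unscheduled visits, for missed scheduled visits or safety or tolerability related reasons are allowed". For an out-of-range laboratory value judged clinically significant, 7.3.5 tells the Investigator: "Repeat the test to verify the out-of-range value". The same section sends some laboratory values to the adverse event record, and 9.4.8 tabulates treatment-emergent events by system organ class and preferred term.

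**The concern.** The harms named in 2.5 are ones that a minority of patients might have. A group mean dilutes a change confined to a few patients, and for electrolytes a fall in some can offset a rise in others. The minimum and maximum show that at least one extreme scheduled value exists. They do not say how many patients had one, or whether those patients were normal at baseline.

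Unscheduled safety visits and repeat tests happen because something looks wrong, so they are likely to hold informative values. The rule in 9.4.7 makes no exception for them beyond the last value of a period.

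At stake is a basic safety question on a primary objective: what proportion of patients on tenapanor, and on sevelamer, had a bicarbonate, potassium or blood pressure value outside stated limits?

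**Working it through.** **When chemistry is drawn.** The schedule of events (1.3) places clinical laboratory tests at Screening and Days 1, 85, 183, 267 and 365. That is 6 draws and agrees with the 6 chemistry samples in Table 8-1. Post-baseline, 4 remain, 2 of them in the 26-week period (Days 85 and 183). Visits 6 to 9 list serum phosphorus but no chemistry panel (8.4, 8.5). The first scheduled post-baseline panel therefore comes 85 − 1 = 84 days, or 12 weeks, after randomization. For a patient still in the study, any bicarbonate or potassium value before then is unscheduled. Under 9.4.7 it is listed only, because the Day 85 or Day 183 value will normally be the later one.

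**When blood pressure is taken.** It is taken at every visit (7.3.2). In the 26-week period both arms have 8 post-baseline readings (Visits 6 to 13). In the withdrawal period the tenapanor-origin patients have 6 (Visits 14 to 19), but the sevelamer patients have 3 (Visits 15, 17 and 19), as they skip Visits 14, 16 and 18.

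**Routes by which an abnormal value can reach a table:**

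| Source of the value | By-visit summary | Adverse event table | Objective patient count |
|---|---|---|---|
| Scheduled laboratory value | Yes | If 7.3.5 is met | No |
| Unscheduled or repeat laboratory value, not last in period | No (listing) | If 7.3.5 is met | No |
| Unscheduled laboratory value, last in period | Can be used | If 7.3.5 is met | No |
| Scheduled blood pressure | Yes | General reporting only | No |
| Unscheduled blood pressure, not last in period | No (listing) | General reporting only | No |

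The last column is empty throughout.

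**Size, as an illustration.** The documents give no incidence, shift or SD for these measures and no power figure for safety, so there is no plan figure to reproduce. Group sizes are from 9.2: about 420 v 140. With 30% lost they are 420 × 0.70 = 294 and 140 × 0.70 = 98; applying that loss to the control arm is my assumption. Also assumed: change has SD 1, 5% of tenapanor patients shift by 2 SD, nobody else shifts, and abnormal means a fall of 2 SD or more.

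- Mean shift: 0.05 × 2 = 0.10 SD. Patients affected: 0.05 × 420 = 21, or 0.05 × 294 ≈ 15.
- If 5% rise and 5% fall by 2 SD, the mean change is 0, while the SD widens from 1 to √(1 + 0.10 × 4) = 1.18.
- Proportion past the cut: 2.28% on control; on tenapanor 0.95 × 2.28% + 0.05 × 50% = 4.66%. Expected counts are 19.6 of 420 and 3.2 of 140.
- Difference 2.39 points; SE = √(0.0466 × 0.9534/420 + 0.0228 × 0.9772/140) = 0.0163; approximate 95% CI −0.8 to 5.6 points.

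**Does counting raise power?** For the mean, SE = √(1.19/420 + 1/140) = 0.0999, where 1.19 = 1 + 0.05 × 0.95 × 4 is the tenapanor variance. Power = Φ(0.10/0.0999 − 1.96) = 17%. For the proportion, the pooled null SE is 0.0193, so power = Φ((0.0239 − 1.96 × 0.0193)/0.0163) ≈ 20%. Other cases, by the same formulas:

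| Affected, shift | 420 v 140: mean / proportion | 294 v 98: mean / proportion |
|---|---|---|
| 2%, 2 to 3 SD | 6–9% / 7–12% | 5–7% / 5–9% |
| 5%, 2 to 3 SD | 17–31% / 20–45% | 13–23% / 14–31% |
| 10%, 2 to 3 SD | 50–80% / 56–93% | 38–65% / 39–79% |

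The gain is small at a 2 SD shift, larger at 3 SD, and depends wholly on the assumed shift and cut.

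**The case against.** A fair defence has five parts.

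1. The summaries go beyond mean change. Actual values are summarised too, with SD, median and range, so an extreme scheduled value is visible, and opposing shifts widen the SD even when the mean is zero. This stands. It shows that an extreme exists, but not how many patients had one.

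2. Unscheduled values are not discarded. They are listed, and they are analysed when last in the period. A patient who leaves early should also have the Visit 23 panel, if possible (5.4, 8.14). This stands. The gap concerns patients who continue past an abnormal unscheduled result.

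3. Laboratory abnormalities reach the adverse event tables. Section 7.3.5 covers values that are confirmed and clinically significant, lead to discontinuation, need treatment or meet a seriousness criterion. The last three turn on consequences rather than opinion. This stands in part: the lead-in to that list applies to values that the Investigator considers clinically significant, and the comparison with sevelamer is open label. The section covers laboratory tests only. Low blood pressure has no specific recording rule and relies on general adverse event reporting (7.3.6).

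4. Safety is descriptive here, so power is the wrong yardstick. I agree, and the working shows no dependable power gain.

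5. Section 9.1 refers to a separate SAP, which governs where it differs. Its detailed text was not available for this review, so such tables may already be planned. That limits the finding but does not remove the rule written in 9.4.7.

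A reader might infer that these harms would go unseen, or that unscheduled values appear nowhere. The documents support neither.

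**Conclusion.** As supplied, the plan contains no shift, worst-value or threshold table for bicarbonate, electrolytes or blood pressure, and 9.4.7 bars most unscheduled and repeat values from the summaries. How often the 2.5 risks occur would have to be read from listings and reported adverse events. The timing matters most in the first 12 weeks, when no chemistry panel is scheduled after Day 1.

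This should be corrected because it bears on the first primary objective and on the purpose of the sevelamer arm. On the assumed 5% incidence, about 21 of 420 tenapanor patients would have no objective count. It would be tempting to add that counting makes detection far more likely; the calculation does not support that at a 2 SD shift, where power is 17% for the mean and 20% for the proportion. The point rests on sections 9.4.1, 9.4.7 and 9.4.8 as written, and would shrink to a reconciliation of 9.4.7 if the separate SAP already has these tables.

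**What to change.** In 9.4.8 and the SAP, for bicarbonate, sodium, potassium, chloride, magnesium and blood pressure, add for each study period:

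1. Shift tables from baseline to the worst post-baseline value, by treatment group, in both directions for electrolytes.
2. The number and percentage of patients with any post-baseline value outside preset limits, tenapanor v sevelamer, with a 95% CI for the difference. Use the central laboratory's reference limits for laboratory tests. For blood pressure, the sponsor fixes the limits before database lock.

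Amend 9.4.7 so that all post-baseline values, including unscheduled and repeat values, count in these tables, while by-visit summaries use scheduled values.

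Repeat the tables on scheduled values only, because unscheduled sampling may differ between arms. For blood pressure in the withdrawal period, restrict that check to Visits 15, 17 and 19, since the scheduled readings are 6 v 3. Keep placebo patients separate in that period.

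If the SAP already contains such tables, bring 9.4.7 into line with it.

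The cost is SAP wording and a few tables from data already collected. No visit, sample or treatment changes.

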## **10 ACCESS TO SOURCE DATA/DOCUMENTS**

The Investigator will provide direct access to source data and documents for the Sponsor or its designee conducting study-related monitoring and/or audits, IRB/ Independent Ethics Committee (IEC) review, and regulatory review. The purpose of an audit or inspection is to systematically and independently examine all study-related activities and documents, to determine whether these activities were conducted, and data were recorded, analyzed, and accurately reported according to the protocol, GCP (Good Clinical Practice), guidelines of the International Conference on Harmonization (ICH), and any application regulatory requirements. The Investigator will contact the Sponsor immediately if contacted by a regulatory agency about an inspection at any clinical site.

The Investigator must inform the study patient that his/her study-related records may be reviewed by the above individuals without violating the patient's privacy of personal health information in compliance with regulations of the Health Insurance Portability and Accountability Act of 1996 (HIPAA).

Attention is drawn to the regulations promulgated by the FDA under the Freedom of Information Act providing, in part, that information furnished to clinical Investigators and IRBs will be kept confidential by the FDA only if maintained in confidence by the Investigator and IRB. By signing this protocol, the Investigator affirms to the Sponsor that the Investigator will maintain, in confidence, information furnished to him or her by the Sponsor and will divulge such information to the IRB under an appropriate understanding of confidentiality with such board.

## **11 QUALITY CONTROL AND QUALITY ASSURANCE**

The Sponsor or its designee will implement and maintain quality control and quality assurance procedures with written SOPs to ensure the study is conducted and data are generated, documented, and reported in compliance with the protocol, GCP, and applicable regulatory requirements.

### **11.1 Conduct of Study**

This study will be conducted in accordance with the provisions of the Declaration of Helsinki and all revisions thereof (Tokyo 2004), and in accordance with the FDA Code of Federal Regulations (21 CFR Parts 11, 50, 54, 56, 312) and the International Conference on Harmonization (ICH) Guidelines on good clinical practice (ICH E6 R2). Specifically, this study is based on adequately performed laboratory and animal experimentation; the study will be conducted under a protocol reviewed by an IRB or IEC; the study will be conducted by scientifically and medically qualified persons; the benefits of the study are in proportion to the risks; the rights and welfare of the patients will be respected; the physicians conducting the study do not find the hazards to outweigh the potential benefits; and each patient will give his or her written, informed consent before any protocol-driven tests or evaluations are performed.

The Investigator may not deviate from the protocol without a formal protocol amendment having been established and approved by an appropriate IRB, except when necessary to eliminate immediate hazards to the patient. Any deviation may result in the patient having to be withdrawn from the study, and may render that patient non-evaluable.

### **11.2 Protocol Amendments**

Only the Sponsor may modify the protocol. All amendments that have an impact on patient risk or the study objectives, or require revision of the ICF, must receive approval from the IRB prior to their implementation. Should the protocol changes be significant i.e., where there are changes in the existing protocol that significantly affect safety of patients, scope of the investigation, or scientific quality of the study, the Sponsor must submit the protocol to the FDA prior to the protocol amendment being implemented.

### **11.3 Monitoring of Study**

The Investigator will permit the site monitor to review study data as frequently as is deemed necessary to ensure data are being recorded in an adequate manner and protocol adherence is satisfactory.

The Investigator will provide access to the source documents or provide certified copies of the medical records for the monitor to verify eCRF entries. The Investigator is expected to cooperate with the Sponsor/designee in ensuring the study adheres to GCP requirements.

The Investigator may not recruit patients into the study until Sponsor or its designee has conducted a detailed review of the protocol and eCRF with the site staff. With agreement of Sponsor, attendance at an Investigator meeting may fulfill this requirement.

#### **11.4 ETHICS**

#### **11.5 Institutional Review Board/Independent Ethics Committee Approval**

##### **11.5.1 Ethics Review Prior to Study**

The Investigator will ensure that the protocol and consent form are reviewed and approved by the appropriate IRB prior to the start of any study procedures. The IRB will be appropriately constituted and will perform its functions in accordance with FDA regulations, ICH GCP guidelines, and local requirements as applicable.

##### **11.5.2 Ethics Review of other Documents**

In addition, the IRB will approve all protocol amendments (except for Sponsor-approved logistical or administrative changes), written informed consent documents and document updates, patient recruitment procedures, written information to be provided to the patients, available safety information, information about payment and compensation available to patients, the Investigator's curriculum vitae and/or other evidence of qualifications, and any other documents requested by the IRB and regulatory authority as applicable.

#### **11.6 Written Informed Consent**

The nature and purpose of the study will be fully explained to each patient (or the patient's legally responsible guardian). The patients must be given ample time and opportunity to inquire about details of the trial, to have questions answered to their satisfaction, and to decide whether to participate. Written informed consent must be obtained from each patient (or guardian) prior to any study procedures being performed.

## **12 DATA HANDLING AND RECORD KEEPING**

### **12.1 Data Reporting and Case Report Forms**

#### 12.1.1 Case Report Forms

The Investigator will be provided with eCRFs, and will ensure all data from patient visits are promptly entered into the eCRFs in accordance with the specific instructions given. The Investigator must sign the eCRFs to verify the integrity of the data recorded.

#### 12.1.2 Laboratory Data

A list of the normal ranges for all laboratory tests to be undertaken forms part of the documentation to be collated prior to trial start. If a central laboratory has been selected to conduct any or all tests, it is essential all samples be analyzed at that laboratory. The Investigator must maintain source documents such as laboratory reports and complete history and physical examination reports.

#### 12.1.3 Retention of Source Documents

The Investigator must maintain source documents such as laboratory reports, x-rays, ECGs, consultation reports, and complete history and physical examination reports.

### **12.2 Retention of Essential Documents**

Essential documents should be maintained for at least 11 years based upon the Sponsor's requirements and may be required to be maintained longer based upon applicable regional regulatory requirements. The Investigator/institution should take measures to prevent accidental or premature destruction of these documents. Should the Investigator/institution not be able to maintain the records for this period of time, the Investigator/institution must inform the Sponsor in writing, via certified mail, at least 90 days prior to the destruction of any study documents, so that the Sponsor has the option, at the Sponsor's expense, to have the records stored for a longer period of time. It is the responsibility of Sponsor to inform the Investigator/institution as to when these documents no longer need to be retained.

### **13 ADMINISTRATIVE INFORMATION**

[REDACTED]

[REDACTED]

[REDACTED]

[REDACTED]

[REDACTED]

